## 5.12.5.6 Minimal Residual Disease (MRD)

MRD assessments using multiparameter flow cytometry will be performed on all bone marrow biopsy samples.

## 5.12.5.7 Disease Assessments and Response Criteria

Disease assessments will be performed on a routine basis according to standard of care practices. This involves blood tests, and when indicated, bone marrow biopsies.

Relapse definition will be based on the LeukemiaNet guidelines: >5% blasts in the bone marrow, reappearance of blasts in the peripheral blood or development of extramedullary disease.

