## 2 SCHEDULE OF STUDY ASSESSMENTS\*

		PF- 04449913	Hx/PE	Hematology	Chemistry	Screening Labs & Procedures	12-Lead EKG	MRD	BM Bx
Screening†			Х	Х	Х	Х	Х		
	Days 1-28	Х							
Cycle 1	Day 1		X	X¶	X¶		Х		
	Day 15		Х	Х	Х		Х		
	Day 28 ‡		Х	Х	Х				
Cycles 2 - 12	Days 1-28	Х							
	Day 1 ‡		Х	Х	Х		X †*		
Initiation of New Azole Antifungal Medication							X ¶*		
Post-transplant day 80 +/- 10 days								Х	Х
Post-transplant day 175 +/- 15								Х	Х
Post-transplant day 365 +/- 30								Х	Х

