## 3 INTRODUCTION

Hematopoietic stem cell transplantation (HSCT) is the only therapy with curative potential for high risk patients with acute myeloid leukemia (AML) However, disease relapse remains the main cause of treatment failure and death after HSCT, suggesting that even highly ablative therapies and the generation of immunological graft versus leukemia responses are very often unable to target the leukemia stem cell population and achieve the requisite cure. At relapse, salvage maneuvers such as secondary transplantations or donor lymphocyte infusions are highly toxic and seldom effective, highlighting the need for tolerable therapies in this population.

Predicting imminent relapse in the post-transplant setting is becoming increasingly sophisticated. In post-transplant patients, flow-cytometry based minimal residual disease (MRD) detection for AML has been shown to be highly predictive of relapse and overall survival (OS). Molecular analyses of leukemia fusion genes can also allow for disease monitoring in select patients, and persistence of a cytogenetic abnormality at the time of transplantation is a poor predictor for relapse and OS after a myeloablative HSCT.

Developing clinical trials for AML post-allogeneic HSCT patients with imminent or high-risk of relapse is an area of active interest that warrants further exploration using novel therapies.

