## 5.2 Study Endpoints

## 5.2.1 Primary Endpoint

• One year relapse-free survival

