## 5.9.2 Prohibited Concomitant Therapy

Chemotherapy, immunotherapy and radiotherapy are prohibited.

The following information is based on results from in vitro studies with PF-04449913 and a drug-drug interaction study with a strong CYP3A4/5 inhibitor in healthy subjects.

CYP3A4/5 Inhibitors: Because inhibition of CYP3A4/5 isoenzymes were expected to increase PF-04449913 exposure and the extent of this interaction in humans was unknown, the use of moderate/strong CYP3A4/5 inhibitors was previously prohibited. In a healthy volunteer study, ketoconazole, a potent CYP3A4/5 inhibitor, produced a 2.4fold increase in plasma exposure and a 1.4-fold increase in peak plasma concentration of PF-04449913. Therefore a potential exists for drug-drug interactions with CYP3A4/5 inhibitors, and co-administration of PF-04449913 in combination with moderate/strong CYP3A4/5 inhibitors is not recommended. Selection of concomitant medication with no or minimal CYP3A4/5 inhibition potential is recommended. Moderate CYP3A4/5 inhibitors (Table 1) should be used with caution and only if considered medically necessary. If a moderate/strong CYP3A4/5 inhibitor is to be initiated in addition to PF-04449913, the guidance provided in Section 5.12.5.5 requiring additional EKG monitoring before, during and after starting the medication, electrolyte monitoring (including correction and re-checking values) and dose

modifications for QTcF prolongation per Section 5.10.2.2 must be followed. Azole antifungals are permitted to be administrated concomitantly with PF-04449913.

**CYP3A4/5 Inducers:** PF-04449913 metabolism may be induced when taking CYP3A4/5 inducers, resulting in reduced plasma concentrations. The impact of CYP3A4/5 inducers on PF-04449913 pharmacokinetics has not been studied in the clinic. Therefore co-administration of PF-04449913 in combination with any moderate/strong CYP3A4/5 inducers (representative medications in Table 1) is not permitted from study entry until study treatment discontinuation.

**Drugs with known risk of Torsade de Pointes (TdP):** PF-04449913 has been shown to have the potential to prolong the QTc interval in pre-clinical studies. In the first-in-patient study as single agent, Grade 3 QTcF prolongation was observed at the highest doses tested (400 mg and 600 mg). While the current clinical dose being

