### 5.14 Statistical Methods and Sample Size Determination

The one-year probability of relapse-free survival for high-risk patients is roughly 30%. Using this as a null hypothesis, and speculating that the use of PF-04449913 will increase the one-year probability of relapse-free survival to 50%, we will require 50 patients to allow for a 90% power to detect this 20% difference, with a significance level of 0.05. We predict the need to screen roughly 60 patients to enroll 50 with high risk of relapse.

Kaplan-Meier estimates using SAS software will be utilized for statistical analysis.

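### The plan does not say how anti-leukemic therapy started before morphologic relapse is handled in one-year relapse-free survival

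*Combined protocol and SAP*

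**What the plan says.** Section 5.2.1 gives the primary endpoint by name only: "One year relapse-free survival". It lists no events and no censoring rules. Section 5.12.5.7 defines relapse as ">5% blasts in the bone marrow, reappearance of blasts in the peripheral blood or development of extramedullary disease", and the individual stopping rules in Section 5.10.1.1 use essentially the same criteria. Minimal residual disease (MRD) is neither a relapse criterion nor a listed reason to stop treatment.

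MRD is nevertheless measured. The Section 2 schedule places it with the marrow biopsies, starting at "Post-transplant day 80 +/- 10 days" and again around days 175 and 365. Section 5.12.5.6 applies it to every marrow sample. The study is open label, and no section withholds the results from treating physicians.

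On other therapy, Section 5.9.2 states "Chemotherapy, immunotherapy and radiotherapy are prohibited", and Section 5.3.2 excludes concomitant anti-neoplastic agents apart from intrathecal prophylaxis. Donor lymphocytes and second transplant are named only in the Section 3 background.

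Section 5.14 sets the benchmark ("The one-year probability of relapse-free survival for high-risk patients is roughly 30" percent), the target ("increase the one-year probability of relapse-free survival to 50" percent) and the size: "we will require 50 patients to allow for a 90% power to detect this 20% difference, with a significance level of 0.05". The efficacy analysis is a single sentence naming Kaplan-Meier estimates. After the last dose, Sections 5.4 and 5.12.4 provide 30 days of follow-up and then annual phone calls, whose content is not specified.

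**The concern.** A positive MRD result at day 80 or 175 could lead a physician to treat before blasts appear. Section 3 itself calls post-transplant flow MRD highly predictive of relapse. If that patient comes off PF-04449913, receives another therapy and remains blast-free at one year, no criterion in Section 5.12.5.7 has been met. On a literal reading the patient is a success, although another treatment may have produced the result.

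The trial has one arm and compares it with a fixed 30%. No control group shares the effect, so each such patient moves the estimate directly toward the conclusion that the drug prevents relapse.

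The other obvious handling, censoring at the start of new therapy, has its own problem. Patients treated for rising MRD are likely to be those nearest to relapse, so the censoring would carry information about outcome and tend to inflate the Kaplan-Meier estimate. Because the text is silent, the choice among event, censoring and no action could be made after open-label results have been seen.

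**Working it through.** **Inputs from the documents.** Null one-year RFS 30%, target 50%, N = 50, power 90%, significance level 0.05 with sidedness not stated (all Section 5.14).

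**Inputs that are assumptions.** The number of rescued patients, the success rate of rescue, and whether the 30% benchmark already contains rescues. The documents give none of these.

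**Step 1: reproduce the plan's sample size.** Treat one-year RFS as a binomial count X out of 50 and find the smallest cut-off with one-sided exact error at or below 0.05.
- P(X ≥ 20 | 50, 0.30) = 0.0848, too large.
- P(X ≥ 21 | 50, 0.30) = 0.0478.
- P(X ≥ 21 | 50, 0.50) = 0.8987, which rounds to 90%.

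The one-sided normal approximation agrees: [(1.645 × √(0.3 × 0.7) + 1.282 × √(0.5 × 0.5)) / 0.2]² = 48.6, so 49. A two-sided 0.05 test would need 60. The stated 50 therefore reproduces as a one-sided, single-stage test with success at 21 or more of 50. That cut-off is derived here; the plan states no decision rule.

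**Step 2: effect of a few rescued patients when the drug is inactive.** Let m of 50 be patients who would have failed but are held relapse-free by other therapy and counted as successes. The expected rate becomes 0.30 + m/50, and the chance of a false success is P(X ≥ 21 | 50, 0.30 + m/50).

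| m | Expected RFS | Chance of ≥ 21 of 50 |
|---|---|---|
| 0 | 30% | 4.8% |
| 1 | 32% | 8.8% |
| 2 | 34% | 14.8% |
| 3 | 36% | 22.9% |

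**Step 3: vary how often rescue is tried and how often it works.** Let f be the share of all patients who would have failed and who start other therapy early, and s the share of those who then stay relapse-free. The expected rate is 0.30 + f × s. The table shows the chance of a false success.

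| s | f = 10% | f = 15% | f = 20% |
|---|---|---|---|
| 50% | 18.6% | 30.2% | 43.9% |
| 25% | 10.1% | 14.0% | 18.6% |
| 10% | 6.6% | 7.6% | 8.8% |
| 5% | 5.6% | 6.1% | 6.6% |

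For example, f = 20% and s = 25% give 0.30 + 0.05 = 0.35, hence 18.6%.

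**Step 4: dependence on the benchmark.** Steps 2 and 3 assume a 30% figure with no comparable rescues. If the historical cohorts contained the same share of rescues, an inactive drug with rescues would still give 30%, and the risk would stay at 4.8%. Partial inclusion falls between.

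**Step 5: what counting new therapy as an event does.** With a rescue-free benchmark, the false-success risk returns to 4.8%. If the 50% target includes rescued patients and the event-counting version had to pass the same cut-off, power would be P(X ≥ 21 | 50, 0.50 − x), where x is the rescued share. It falls from 89.9% to 83.9%, 76.0% or 66.3% for x = 2%, 4% or 6%.

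**The case against.** Four points on the other side have force.

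First, a reader might infer that the plan counts rescued patients as relapse-free and credits the drug with other treatments' successes. The documents do not say so. They name the endpoint and the Kaplan-Meier method and stop there. Such a patient could be kept as event-free, censored or counted as failed. What stands is that the handling is unspecified.

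Second, the route is narrow. Sections 5.9.2 and 5.3.2 bar other anti-leukemic treatment alongside study drug, noncompliance can end participation, and MRD is not a stopping criterion. The scenario needs a deviation, a withdrawal, or a decision to take a patient without morphologic relapse off drug. That limits frequency but does not close the gap: Sections 5.10.1.1 and 5.11 allow patient or physician discontinuation, and nothing classifies therapy given afterwards.

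Third, Section 3 mentions "salvage maneuvers such as secondary transplantations or donor lymphocyte infusions" only as treatment at relapse, and calls it highly toxic and seldom effective. It is no evidence that early rescue happens in this trial, and it supports no particular success rate. Equally, it concerns overt relapse, so it does not show that earlier treatment would fail.

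Fourth, concomitant medications are reviewed at visits (Section 2) and concurrent treatments are summarised (Section 5.15), so capture during treatment partly exists. Neither is tied to RFS, and neither secures dates and types of therapy after drug stops.

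**Conclusion.** The gap is certain and its size is not. No section makes anti-leukemic therapy before morphologic relapse an event, a censoring point or a recorded non-event in one-year RFS, and no section secures its capture once study drug has stopped.

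Under an inactive drug, a rescue-free 30% benchmark and the derived cut-off of 21 of 50, false-success risk goes from 4.8% to 8.8%, 14.8% or 22.9% with one, two or three rescued patients in 50. It is smaller if the benchmark includes rescues. The top of the Step 3 range, 43.9%, should not be read as a forecast: it needs one patient in five to be treated early and half of those to succeed, and the documents support neither figure. This is a cheap improvement that protects a single-arm conclusion, not proof that the primary result will be biased.

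**What to change.** Make three changes:

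- Record the start date and type of any non-protocol anti-leukemic therapy (chemotherapy, donor lymphocytes, radiotherapy, second transplant) through the one-year endpoint, including after study drug is stopped.
- Add to Section 5.14 a pre-specified supportive Kaplan-Meier analysis of RFS in which the start of such therapy before morphologic relapse counts as an event.
- Report it beside the primary result with the number of patients affected, and interpret the relapse-prevention claim in light of both.

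The relapse definition in Section 5.12.5.7 stays as it is, and no treatment rule changes. The supportive analysis should not become a second hurdle that must also clear 30%; Step 5 shows what that could cost in power.

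The cost is some added data collection after drug stops, because 30 days of follow-up plus annual calls may not yield dated therapy and relapse status to one year. The supportive estimate may also be lower than the primary, partly because it counts as failures some patients who would have stayed relapse-free without the added therapy.

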#### 5.12.5.8 Correlative Assessments

Tissue will be banked for future testing and correlative studies. Each participating institution will employ their own IRB-approved tissue banking protocol for this purpose.

# 5.13 Definitions and Reporting Procedures for Adverse Events

Subjects will be evaluated for AEs at each visit with the NCI-CTCAE version 4.03 used as a guide for the grading of severity. All adverse clinical experiences, whether observed by the investigators or reported by the patient, must be recorded, with details about the duration and intensity of each episode, the action taken with respect to the study, and the patients' outcomes. The investigators will evaluate each AE for its severity and its relationship to the study. The investigators will appraise all abnormal laboratory results for their clinical significance. If any abnormal laboratory result is considered clinically significant, the investigators will provide details about the action taken with respect to the study and the patients' outcomes.

## 5.13.1 Definitions of Adverse Events

## 5.13.1.1 Adverse Event

According to the International Conference on Harmonization of Technical Requirements for Registration of Pharmaceuticals for Human Use (ICH) Guidelines (Federal Register. 1997;62(90):25691-25709), Title 21 of the US Code of Federal Regulation (CFR) 312.32, and Investigational New Drug (IND) Safety Reports, an AE is defined as follows:

"Any untoward medical occurrence in a subject or clinical investigational subject administered a pharmaceutical product and which does not necessarily have a causal relationship with this treatment. An AE can therefore be any untoward medical occurrence regardless of relationship to the medicinal (investigational) product."

Abnormal laboratory values for laboratory parameters specified in the study should not be recorded as an AE unless an intervention is required (repeat testing to confirm the abnormality is not considered an intervention), the laboratory abnormality results in a SAE, or the AE results in study termination or interruption/discontinuation of study treatment. Medical conditions present at screening (i.e.: before the study treatment is administered) are not SAEs and will not be recorded on SAE pages of the case report forms. These medical conditions will be adequately documented in the patient chart. However, medical conditions present at baseline that worsen in intensity or frequency during the treatment or post-treatment periods will be reported and recorded as AEs.

### 5.13.1.2 Serious Adverse Event (SAE)

An AE will be classified as an SAE if it meets one of the following criteria (Reporting see section 5.13.4 and Appendix B):

Fatal:	AE resulted in death.
Life threatening:	The AEs placed the patient at immediate risk of death. This classification does not apply to an AE that hypothetically might cause death if it were more severe.
Hospitalization:	AE that required or prolonged inpatient hospitalization. Hospitalizations for elective medical or surgical procedures or treatments planned before enrollment in the treatment plan or routine check-ups are not SAEs by this criterion. Admission to a palliative unit or hospice care facility is not considered to be a hospitalization.
Disabling/incapacitating:	AE resulted in substantial and permanent disruption of the patient's ability to carry out normal life functions.
Congenital anomaly or birth defect:	An adverse outcome in a child or fetus of a patient exposed to the treatment regimen before conception or during pregnancy.
Medically significant:	The AE did not meet any of the above criteria, but could have jeopardized the patient and might have required medical or surgical intervention to prevent one of the outcomes listed above.

#### 5.13.1.3 Pregnancies

Pregnancies and suspected pregnancies (including a positive pregnancy test regardless of age or disease state) of a female subject occurring while the subject is on PF-04449913, or within 28 days of the subject's last dose of, are considered immediately reportable events. PF-04449913 is to be discontinued immediately, and the patient will discontinue the study.

For investigational products and for marketed products, an exposure during pregnancy (also referred to as exposure inutero) occurs if:

- A female becomes, or is found to be, pregnant either while receiving or being exposed (e.g., due to treatment or environmental exposure) or after discontinuing or having been directly exposed to the investigational product
- A male has been exposed (egg, due to treatment or environmental exposure) to the investigational product prior to or around the time of conception or is exposed during his partner's pregnancy.

If the outcome of the pregnancy meets the criteria for an SAE (i.e., ectopic pregnancy, spontaneous abortion, intrauterine fetal demise, neonatal death, or congenital anomaly [in a live born, a terminated fetus, an intrauterine fetal demise or a neonatal death]), the investigator should follow the procedures for reporting SAEs.

All neonatal deaths that occur within 28 days of birth should be reported, without regard to causality, as SAEs. In addition, any infant death after 28 days that the Investigator suspects is related to the in utero exposure to PF-04449913 should also be reported.

# 5.13.2 Relationship of the Adverse Event to Treatment

The investigator will evaluate the relationship of each AE to study treatment using the following criteria:

Fatal:	AE resulted in death.
Unrelated:	Another cause of the AE is more plausible, a temporal sequence cannot be established with the onset of the AE and administration of the treatment, or a causal relationship is considered biologically implausible.
Possibly Related:	There is a clinically plausible time sequence between onset of the AE and administration of treatment, but the AE could also be attributed to concurrent or underlying disease, or the use of other drugs or procedures. Possibly related should be used when treatment is one of several biologically plausible AE causes.
Definitely Related:	The AE is clearly related to use of the treatment.

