# 5.10.1 Stopping Rules

## 5.10.1.1 Individual Patients' Stopping Rules

Patients may be terminated from the study for the following:

- Noncompliance with the study protocol
- Morphological disease relapse, defined as having a bone marrow biopsy with > 5% leukemic blasts on the aspirate differential, the presence of peripheral blood blasts or extramedullary disease
- Patient decides to withdraw from the study
- ≥ Grade 3 AE that is possibly related to the study drug and does not resolve or improve within 28 days (see Section 5.10.2.2)
- Serious AE (SAE) related or possibly related to the study drug; disabilities, hospitalizations, prolongation of

hospitalizations or required interventions that are related to the transplant are excepted

- Development of unrelated illness which compromises further participation in the study
- Investigator determines that continuation on study is no longer in the best interest of the patient or a change in the patient's condition renders them ineligible for further treatment
- Subject is lost to follow-up despite reasonable efforts by the investigator to locate the subject.

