## 5.10.1.2 Study Stopping Rules

The study will be suspended pending further review if, at any time, there is sufficient evidence to suggest that the true probability of hematopoietic toxicity attributable to the drug exceeds 25% or the true probability of severe GVHD exceeds 25%. Sufficient evidence will be defined as an observed failure rate whose lower one-sided 80% confidence limit exceeds the thresholds listed above (25% for hematopoietic toxicity and GVHD). Operationally, the study will be suspended if any of the following proportions are observed (or exceeded): 3/3-5, 5/6-10, 7/11-15, 9/16-20, 10/21-25, 11/26-28. The probabilities of early termination based on this stopping rule for various rates of true toxicity are shown in the table below. The probabilities are based on a simulation with 1,000 replications.

	Probability of Early Stopping Due to Toxicity				
Number of Patients	True Toxicity Rate				
	15%	25%	35%	45%	
28	0.0016	0.0693	0.375	0.787	

- If any of the above stopping rules is met upon enrollment of the next patient, accrual will be held until it is determined that no stopping rules will be met with currently enrolled patients.
- The study will continue until the last patient is followed 30 days beyond receiving the last dose of study drug. Annual

phone calls will be made as appropriate for 5 years after discontinuation of the study.

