# 5.11 Study Completion and Termination

Study patients who have met any of the following endpoints will have completed the study:

- SAE related to the study drug
- Disease relapse
- Death

Study patients may be prematurely terminated from the study for the following reasons:

- Physician and/or patient decides to discontinue treatment for reasons other than an AE
- ≥ Grade 3 related or possibly related non-hematologic AE or grade 4 related or possibly related hematologic toxicity that does not resolve or improve within 28 days
- Noncompliance with the study protocol
- Development of unrelated illness which compromises further participation in the study
- The patient is lost to follow up (no further data collection or submission will be expected)
- The patient withdraws consent (no further data collection or submission will be expected)

At termination, both concomitant medications and ongoing AEs are to be recorded, including any new AEs reported at the end of the study. Any unresolved AE at discontinuation of the study treatment should be followed until they have resolved or stabilized. Patients may choose to stop study treatment for any reason without jeopardizing their relationship with healthcare providers.

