### 5.13.3 Procedures for Recording Adverse Events

#### 5.13.3.1 Information to be Collected

Whether considered related or not, during the reporting period, all SAEs and non-serious AEs are to be recorded on an AE case report form (CRF). Patients who terminate the study early will be followed for 30 days after the last dose of study treatment for AEs and SAEs. Patients who experience a non-serious AE considered to be possibly or definitely related to study treatment will be followed until all significant changes have returned to baseline or stabilized, the patient dies, or the patient withdraws consent. All SAEs will be followed as described, regardless of their relationship to study treatment. During the reporting period, the following information should be collected:

- Description of the AE, including onset and resolution dates
- Relationship to treatment plan, treatment or other causality
- Action taken, including use of concomitant medications
- If the event is serious, note all criteria that apply

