### 5.13.3.2 Recording Serious Adverse Events

- For SAEs, the primary event will be recorded on both an AE CRF and an SAE/Product Complaint Form; events occurring as a result of the SAE will be described on the SAE/Product Complaint Form in the narrative description of the case
- Death is an outcome of an event. The event that resulted in the death will be recorded and reported on both an SAE/Product Complaint Form and on an AE CRF.
- For hospitalizations or surgical or diagnostic procedures, the illness leading to the hospitalization or surgical or diagnostic procedure will be recorded as the SAE, not the procedure itself. The procedure will be captured in the narrative as part of the action taken in response to the illness.

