### 5.13.4.2 Format for Adverse Event Reporting

All AE reports will include the patient's number, age, sex, weight, severity of reaction (mild, moderate, severe), relationship to the study (fatal relationship, definitely related, possibly related, unrelated), date and time of administration of test medications and all concomitant medications, and subsequent medical treatment provided. An investigator-initiated research adverse event form will be utilized for reporting.

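### The causality scale lists Fatal, which is an outcome, so a death can be recorded without a causal grade and its status under the attribution-based rules is undefined (minor correction)

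*Combined protocol and SAP*

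**What the plan says.** Section 5.13.2 introduces its scale with the sentence "The investigator will evaluate the relationship of each AE to study treatment using the following criteria". The four entries that follow are Fatal, Unrelated, Possibly Related and Definitely Related. The last three are defined by timing, plausibility and alternative causes. The whole definition of the first is "AE resulted in death".

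Section 5.13.4.2, on the format of AE reports, asks for "relationship to the study (fatal relationship, definitely related, possibly related, unrelated". Section 5.13.3.1 lists the information to collect for each event and includes "Relationship to treatment plan, treatment or other causality". Section 5.13.3.2 states "Death is an outcome of an event".

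Several rules depend on attribution:

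- Section 5.10.1.2 suspends the study on sufficient evidence that the "true probability of hematopoietic toxicity attributable to the drug exceeds 25" percent.
- Section 5.10.1.1 allows a patient to be taken off study for a "Serious AE (SAE) related or possibly related to the study drug".
- Section 5.11 lists an "SAE related to the study drug" among the events that complete a patient's participation.

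**The concern.** A causality scale should answer one question: how likely is it that the treatment caused the event? Fatal answers a different one, namely how the event ended. With both kinds of answer in one list, an investigator reporting a death can choose the entry that literally fits and leave the causal judgement unmade.

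The causal judgement matters most for deaths. After allogeneic transplantation a death may have several plausible causes, and the Possibly Related entry is written for that situation. If it is skipped, whoever applies a rule worded in terms of related or attributable events must decide after the fact what a Fatal rating means. The plan gives no guidance, and participating institutions could decide differently.

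**Working it through.** There is no stated figure to reproduce, so the check sets the sections side by side.

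1. **Is the entry an extraction error or a single slip?** No. It is in the table in 5.13.2 and again in running prose in 5.13.4.2. Both the rating instruction and the reporting format carry it.

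2. **Does the entry have causal content?** No. The definition in 5.13.2 is word for word the one for the Fatal row in 5.13.1.2. There it is a seriousness criterion, which is a proper use. By that definition every fatal AE qualifies, whatever its cause.

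3. **Is it consistent with the rest of the plan?** No. Section 5.13.3.2 classes death as an outcome and has the event behind it recorded instead.

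4. **Is a second, causal grade required for an event rated Fatal?** No section asks for one. Section 5.13.3.1 requires relationship to be collected, but gives no separate scale for fatal events. It asks staff to note all criteria that apply only for seriousness. Section 5.13.4.2 sets out the relationship terms as a list of alternatives, in the same form as its severity list of mild, moderate and severe. Its list of report items names no outcome field.

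5. **Does any section map Fatal to related, possibly related or attributable?** No. Sections 5.10.1.1, 5.10.1.2, 5.10.2.2 and 5.11 use those terms without saying how a Fatal rating is handled. Two readings are possible:
   - Fatal is not a causal grade, so the event is not counted as related. Drug-related deaths would then be missed.
   - Fatal is the strongest form of relationship, so the event is counted as related. Because every fatal AE meets the definition, deaths with another cause would then be counted too.

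   The order of the lists does not settle it. In 5.13.4.2 the fatal entry stands next to definitely related; in 5.13.2 it stands next to Unrelated.

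6. **Which rules could be affected in practice?** The patient-level rules in 5.10.1.1 and 5.11 have little bearing on a patient who has died, and 5.11 lists death separately. The severe-GVHD limb of 5.10.1.2 does not depend on attribution. That leaves the hematopoietic limb of 5.10.1.2, and any summary by relatedness that may be produced.

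**The case against.** The strongest reply is that the entry is untidy but harmless, for four reasons.

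- **The entries are not stated to be exclusive.** A site could record Fatal together with a causal grade, and 5.13.3.1 asks for causality without exempting deaths. The case report form is not in the documents, so it cannot be seen whether a single choice is forced. This stands, and it is why the finding is that a causal grade *can* be missing, not that it will be.
- **The stopping rule does not cite this scale.** Section 5.10.1.2 speaks of toxicity attributable to the drug, which is not one of the four terms, and nothing says that its count is drawn from this field. This also stands. It leaves open how attribution is determined for a death.
- **Deaths are not lost.** Section 5.13.3.2 puts the event on both an AE form and an SAE form. Section 5.13.4.6 requires SAEs to be reported through 30 days after the last treatment whatever the relationship. Under 5.10.3 the Principal Investigator reviews AEs, outcomes are discussed at least monthly, and the DSMC reviews serious events and can suspend the trial. This stands and limits the consequence considerably.
- **No planned analysis uses relatedness.** The safety endpoint in 5.2.2 is the incidence and severity of AEs, and Sections 5.14 and 5.15 plan no analysis by relationship. A reader might infer that the toxicity objective requires a count of drug-related deaths; the documents do not say so.

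A reader might also infer that the study would wrongly continue. Suppose that, among the first five patients, two have attributable non-fatal hematopoietic toxicities and a third has a drug-related hematopoietic death rated Fatal. Counted as 2, these fall short of the boundary of 3 for three to five patients. The documents do not support that conclusion. It needs the Fatal rating to be the only one given, to be read as not attributable, and to go uncorrected in every review above.

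**Conclusion.** The scale is wrong as written in two sections and conflicts with the plan's own statement that death is an outcome. A fatal event can be recorded without a causal grade, and the plan does not say whether it then counts as related or as attributable under the hematopoietic stopping rule.

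The size cannot be estimated: the documents give no rate at which deaths would be rated this way, and they do not fix the direction of any resulting error. It would go too far to say that deaths drop out of the toxicity counts, since that assumes both a single choice per event and the first of the two readings above. This is a minor correction, worth making because it removes an ambiguity about the gravest events.

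**What to change.** Delete Fatal from the relationship scale in Section 5.13.2 and the fatal relationship term from Section 5.13.4.2. Keep death as a seriousness criterion in 5.13.1.2 and as an outcome, as 5.13.3.2 already has it. Add one sentence requiring a rating of unrelated, possibly related or definitely related for every AE, including those that end in death.

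The cost is a wording change in two sections, plus a matching change to the case report form and adverse event form if they carry the same list, which the documents do not show. It changes no dose, eligibility rule, stopping boundary or sample size.
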